3.1 Rationale for Dosage Selection

The primary objective of the study is to determine a recommended dosage of pacritinib for further clinical development; thus the study is designed to characterize the dose–response relationship for pacritinib in patients with MF. Three dosage levels have been selected based on previous clinical phase 1/2 studies and the phase 3 study PERSIST-2, to span the dose–response curve and allow adequate characterization of dose–response relationships for efficacy and safety of pacritinib. These three dosages include a low dosage (100 mg QD), an intermediate dosage (100 mg BID), and a higher dosage with potentially acceptable efficacy and safety profiles (200 mg BID). As the systemic exposure of pacritinib is linear up to the 300 to 400 mg dosage (see dose-proportionality clinical study report; Study SB1518-2010-004), it is projected that the 100 mg QD regimen would result in pacritinib systemic exposure levels similar to those of a 50 mg BID regimen.

The lowest dosage level selected for the study (100 mg QD) is 4-fold lower than the highest dosage level in the study (200 mg BID) in terms of total daily dose, allowing for adequate separation between dosage levels selected in the study, which should in turn support characterization of the dose–response relationship in the study. The 100 mg QD regimen produced minimal clinical disease responses in 6 patients in phase 1/2 studies and was not associated with any safety concerns, pointing to limited efficacy at the 100 mg QD dosage level. Moreover, integrated exposure-response data from across the clinical program indicate that the exposure-response relationship for pacritinib is relatively steep whereby marked efficacy is only observed at exposure levels higher than those associated with the 100 mg QD

regimen (Figure 1). Median geometric mean C_{min} of pacritinib at steady-state following administration of 200 mg BID regimen in PERSIST-2 was 6,783 ng/mL. Given the observed linearity following singledose administration of pacritinib capsules up to 400 mg, median steady-state C_{min} levels of pacritinib with administration of 100 mg QD would be projected at around 1,700 ng/mL, where there no evidence for efficacy as measured by SVR as evident from the exposure-response relationship for pacritinib (Figure 1). Overall, the 100 mg QD regimen is likely to show minimal efficacy and is a reasonable choice for the lowest dosage in the study. Dosage levels lower than 100 mg QD are unlikely to offer any advantage in terms of better characterization of the dose–response relationship of pacritinib in the study.

Given the observed incidence of SAEs, the 200 mg BID regimen will be the highest dosage studied in the current study. The 200 mg BID regimen has already demonstrated robust efficacy and a potentially acceptable safety profile in the PERSIST-2 study. An intermediate dosage of 100 mg BID will be tested that is likely to have efficacy based on the phase 1 studies and clinical experience in patients who underwent dose reduction in the phase 3 studies.

Based on the efficacy observed in clinical studies in MF to date, the selected dosage levels of pacritinib are projected to provide reasonable likelihood of efficacy responses while allowing for full characterization of the dose–response and dose-safety relationships for pacritinib.

Figure 1. Exposure-response Relationships on Spleen Volume Response for Pacritinib in Phase 1/2 Studies and PERSIST-2 Study

Source: Section 5.3.5.4, PAC-011-03 Exposure-Response Report, Section 5.3.5.4 PAC-011-03 dataset, and Section 5.3.5.4 PAC-011-04 Dose Justification Memo.

3.2 Progression of Disease

Patients may experience one or more of the following: splenic progression, splenic irradiation, splenectomy, or leukemic transformation. All of these events represent progression of disease and must be reported. A patient who has experienced one event will continue to be followed for other progression events through Week 24. Although the date of the first event is considered the date of progression of disease, subsequent events must also be reported.

Progression of disease is defined as one or more of the following:

- Splenic progression, defined as an increase in splenic volume of ≥25% from baseline, based on MRI (preferred) or CT scan
- Splenic irradiation
- Splenectomy
- Leukemic transformation, defined as one or more of the following:
 - Increase in peripheral blood blast percentage to $\geq 20\%$
 - Bone marrow blast count $\geq 20\%$ (bone marrow performed as standard of care)

3.3 Treatment Continuation After Progression of Disease

Patients who have progression of disease on MRI (preferred) or CT scan, defined as an increase in splenic volume of \geq 25% from baseline on MRI or CT scan, will not be allowed to continue study treatment. Patients should continue the visit schedule through Week 24 (including imaging and all protocol-specified study assessments) despite treatment discontinuation or disease progression prior to Week 24, unless patient withdraws consent, dies, undergoes splenic irradiation or splenectomy, or initiates any non-protocol-directed anti-myelofibrosis treatment.

4 Patient Selection and Withdrawal

4.1 Target Population

4.1.1 Inclusion Criteria

- 1. PMF, PPV-MF, or PET-MF (as defined by Tefferi and Vardiman 2008; Appendix 4)
- 2. DIPSS Intermediate-1, Intermediate -2, or High risk (Passamonti et al 2010; Appendix 3)
- 3. Prior ruxolitinib treatment with failure to benefit or intolerance as defined by at least one of the following:
 - a. Treatment for \geq 3 months with inadequate efficacy response defined as <10% spleen volume reduction by MRI or <30% decrease from baseline in spleen length by physical examination or regrowth to these parameters following an initial response; and/or
 - b. Treatment for ≥ 28 days complicated by either:
 - i. Development of a red blood cell transfusion requirement (at least 2 units/month for 2 months)
 - ii. NCI CTCAE grade ≥3 AEs of thrombocytopenia, anemia, hematoma, and/or hemorrhage while being treated with a dosage of <20 mg BID
- 4. Palpable splenomegaly ≥5 cm below the lower costal margin (LCM) in the midclavicular line as assessed by physical examination
- TSS of ≥10 on the MPN-SAF TSS 2.0 or patients with a single symptom score of ≥5 or two symptoms ≥3 including only the symptoms of left upper quadrant pain, bone pain, itching or night sweats (Appendix 3)
- 6. Age ≥ 18 years old
- 7. Eastern Cooperative Oncology Group (ECOG) performance status 0 to 2 (Appendix 6)
- 8. Peripheral blast count of <10% throughout the screening period
- 9. Absolute neutrophil count of $>500/\mu L$
- Adequate liver and renal function, defined by liver transaminases (aspartate aminotransferase [AST]/serum glutamic oxaloacetic transaminase [SGOT] and alanine aminotransferase [ALT]/serum glutamic pyruvic transaminase [SGPT]), ≤3 × the upper limit of normal (ULN) (AST/ALT ≤5 × ULN if transaminase elevation is related to MF), direct bilirubin ≤4× ULN, and creatinine ≤2.5 mg/dL
- 11. Adequate coagulation function, defined by prothrombin time (PT)/international normalized ratio (INR), partial thromboplastin time (PTT), or thrombin time (TT) of $\leq 1.5 \times ULN$
- 12. Left ventricular cardiac ejection fraction (LVEF) of ≥45% by echocardiogram or multigated acquisition (MUGA) scan
- 13. If fertile, willing to use effective birth control methods during the study
- 14. Willing to undergo and able to tolerate frequent MRI or CT assessments during the study
- 15. Able to understand and willing to complete symptom assessments using a patient-reported outcomes instrument
- 16. Provision of informed consent

4.1.2 Exclusion Criteria

- 1. Life expectancy <6 months
- 2. Completed allo-SCT or are eligible for and willing to complete allo-SCT
- 3. History of splenectomy or planning to undergo splenectomy
- 4. Splenic irradiation within the last 6 months
- 5. Previously treated with pacritinib
- 6. Patients receiving high-dose ruxolitinib (more than 10 mg BID or 20 mg QD) who cannot tolerate tapering down ruxolitinib to 10 mg BID or less prior to the first dose of pacritinib as described in Section 6.6
- 7. Treatment with anticoagulation or antiplatelet agents, except for aspirin dosages of ≤100 mg per day, within the last 2 weeks
- 8. Treatment with a strong CYP3A4 inhibitor or a strong cytochrome P450 inducer within the last 2 weeks (Appendix 5 and Appendix 6, respectively)
- 9. Treatment with medications that can prolong the QTc interval within the last 2 weeks (Appendix 8)
- 10. Treatment with an experimental therapy within the last 28 days
- 11. Significant recent bleeding history defined as NCI CTCAE grade ≥2 within the last 3 months, unless precipitated by an inciting event (e.g., surgery, trauma, injury)
- 12. Any history of CTCAE grade ≥2 non-dysrhythmia cardiac conditions within the last 6 months. Patients with asymptomatic grade 2 non-dysrhythmia cardiac conditions may be considered for inclusion, with the approval of the medical monitor, if stable and unlikely to affect patient safety.
- 13. New York Heart Association Class II, III, or IV congestive heart failure (Appendix 7)
- 14. Any history of CTCAE grade ≥2 cardiac dysrhythmias within the last 6 months. Patients with non-QTc CTCAE grade 2 cardiac dysrhythmias may be considered for inclusion, with the approval of the medical monitor, if the dysrhythmias are stable, asymptomatic, and unlikely to affect patient safety.
- 15. QTc prolongation >450 ms or other factors that increase the risk for QT interval prolongation (e.g., heart failure, hypokalemia [defined as serum potassium <3.0 mEq/L that is persistent and refractory to correction], family history of long QT interval syndrome, or concomitant use of medications that may prolong QT interval) (Appendix 8)
- 16. Any active gastrointestinal or metabolic condition that could interfere with absorption of oral medication
- 17. Active or uncontrolled inflammatory or chronic functional bowel disorder such as Crohn's Disease, inflammatory bowel disease, chronic diarrhea, or constipation
- 18. Other malignancy within the last 3 years, other than curatively treated basal cell or squamous cell skin cancer, carcinoma in situ of the cervix, organ-confined or treated nonmetastatic prostate cancer with negative prostate-specific antigen, in situ breast carcinoma after complete surgical resection, or superficial transitional cell bladder carcinoma

- 19. Uncontrolled intercurrent illness, including, but not limited to, ongoing active infection or psychiatric illness or social situation that, in the judgment of the treating physician, would limit compliance with study requirements
- 20. Known seropositivity for human immunodeficiency virus
- 21. Known active hepatitis A, B, or C virus infection
- 22. Women who are pregnant or lactating
- 23. Concurrent enrollment in another interventional trial

4.2 Criteria for Withdrawal of Patients

4.2.1 Withdrawal from Study Treatment and Procedures

Patients may discontinue or be withdrawn from treatment at any time. All reasonable efforts should be made to retain patients who discontinue treatment in the study and to conduct visits through Week 24 required by the protocol, including MRI (preferred) or CT scanning and follow-up for progressive disease, and leukemic transformation. Reasons for discontinuing treatment may include but are not limited to the following:

- Documented disease progression as defined in Section 3.2.
- Unrelated intercurrent illness that, in the judgment of the principal investigator, will affect assessments of clinical status to a significant degree
- Pregnancy
- Patient's decision
- Patient noncompliance with study drug
- Clinical need for concomitant therapy that is not permitted in the study
- Decision on the part of the investigator or CTI BioPharma Corp. medical monitor that it is in the patient's best interest to withdraw from study treatment
- Sponsor decision to terminate study
- Death

5 Method of Treatment Assignment and Blinding

Initially, eligible patients will be centrally randomized in a 1:1:1 allocation ratio to pacritinib 100 mg QD, pacritinib 100 mg BID, or pacritinib 200 mg BID using a central interactive web response system. If interim monitoring analysis indicates that any one of the treatment arm meets the stopping criteria (Section 11.9) for efficacy or safety and is thus dropped, then the randomization will be updated to a 1:1 ratio of the two remaining study arms. In the case of two arms being dropped by interim efficacy or safety monitoring, then all eligible patients will be enrolled to the remaining one active arm until up to 30 evaluable subjects are enrolled for that arm.

Randomization will be stratified by geographic region (North America, Europe, versus rest of the world [ROW]) and baseline platelet count (\leq 50,000/µL; >50,000/µL and \leq 100,000/µL; and >100,000/µL). The most recent platelet count obtained prior to start of treatment will be the basis of stratification by baseline platelet count.

A patient's treatment assignment will be known to all except the independent radiographic and cardiology assessors who will remain blinded to patient treatment assignment throughout the study.

6 Study Treatment

6.1 Study Drug Administration

Patients will be supplied with 100 mg capsules of the drug. If assigned to the once per day dosing arm, patients will take 100 mg (1 capsule) of pacritinib QD, at the same time of day, orally, with or without food. Patients assigned to twice per day dosing will take 100 mg (1 capsule) of pacritinib BID at the same times of day, orally, with or without food or 200 mg (2 capsules) of pacritinib BID orally, at the same times of day, with or without food (Table 2).

Table 2.	Study Treatment Schedule
----------	---------------------------------

Treatment	Dosage/Regimen
Pacritinib 100 mg QD	Pacritinib 100 mg (1 capsule) QD orally, at the same time of day, with or without food
Pacritinib 100 mg BID	Pacritinib 100 mg (1 capsule) BID orally, at the same time of day, with or without food
Pacritinib 200 mg BID	Pacritinib 200 mg (2 capsules) BID orally, at the same time of day, with or without food

6.2 Study Drug Description and Storage

Pacritinib for oral administration is supplied in capsules containing 100 mg (as the free base) in red cap/gray body size 0 opaque hard gelatin capsules. The inactive ingredients are microcrystalline cellulose, magnesium stearate, and polyethylene glycol 8000.

Each capsule contains 146 mg of pacritinib citrate, which is equivalent to 100 mg pacritinib free base.

Pacritinib capsules should not be opened or crushed. Direct contact of the powder in pacritinib capsules with the skin or mucous membranes should be avoided. If such contact occurs, affected areas should be washed thoroughly with water.

Pacritinib capsules should be stored at controlled room temperature 20°C to 25°C or 68°F to 77°F, with excursions allowed from 15°C to 30°C or 59°F to 86°F. All pacritinib supplies must be kept in a restricted-access area.

6.3 Dosage, Route, and Mode of Administration

Patients in each arm will be supplied with 100-mg capsules of pacritinib. If assigned to the twice per day dosing arms, patients will either take 100 mg (1 capsule) or 200 mg (2 capsules) of pacritinib twice per day, orally, at the same time of day, with or without food. On days when PK and PD samples and ECGs are to be obtained, pacritinib will be administered in the clinic.

6.4 Drug Accountability

At every study visit, patients will return bottles in which pacritinib is supplied with all remaining untaken pacritinib capsules, if any. Patient compliance will be evaluated by pill count.

6.5 Pacritinib Treatment Adjustments for Adverse Events

6.5.1 Treatment Interruption and Discontinuation

Safety parameters including AEs, hematology, cardiac monitoring, and serum chemistry will be assessed according to the protocol. Pacritinib treatment may be withheld for up to 7 days due to drug-related toxicities. A longer recovery period may be allowed based on the toxicity, but must be agreed upon between the investigator and medical monitor.

Pacritinib should be withheld 7 days prior to planned invasive procedures and concurrently with any unplanned invasive procedure. Pacritinib may be restarted after 2 days without active signs or symptoms of active bleeding.

After treatment interruption, patients may resume pacritinib treatment per dose management guidelines below.

6.5.2 Dosage Management Guidelines for Hematologic Toxicity and Related Complications

Myelosuppression is common in patients with MF and this study allows enrollment of patients with severe cytopenias. Patients with complications of myelosuppression may receive standard supportive care, including transient use of granulocyte-colony stimulating factor for the treatment of febrile neutropenia and red blood cell and platelet transfusion as clinically indicated. Patients receiving pacritinib are not allowed to receive erythropoietin for the treatment of anemia or platelet stimulating factors for the treatment of thrombocytopenia.

Hematology parameters, including CBC, differential, and platelet count will be evaluated at regular intervals during the study. These parameters should be monitored more frequently if clinically required. Patients with a baseline platelet count of $\leq 50,000/\mu$ L must be monitored weekly by central laboratory assessment for the first 8 weeks, then monthly if counts remain $\leq 50,000/\mu$ L. Unscheduled local laboratory test results may be used for assessment and management of patients in real time. Samples collected for local testing must also be submitted to the central laboratory and the results captured in the clinical database.

Table 3 indicates required dose interruptions and modifications for hematologic toxicities and complications such as hemorrhage and febrile neutropenia. Of note, if more than one toxicity is experienced simultaneously, the higher-grade toxicity should determine the dose interruption/modification.

Event	CTCAE Grade	Management/Action
Thrombocytopenia	 ≥ 2 grade decrease in platelets to grade 3 or 4 	 Hold pacritinib for up to 7 days until recovery of platelet count to ≤ grade 2. Restart at the next lower dose level. If at 100 mg QD dose level, discontinue.
	• For patients starting treatment with grade 3 thrombocytopenia who progress to grade 4 thrombocytopenia that lasts at least 14 days or is complicated by hemorrhage or a new platelet transfusion requirement	 Pacritinib may be held for up to 7 days at the treating physician's discretion until recovery of platelets to baseline. Restart either at the same dose or at the next lower dose level.

Table 3	Treatment Toxicit	v and Dosage Mana	agement: Hematologic	Toxicities and Rela	ted Complications
I able J.	Treatment Toxicit	y anu Dusage Mana	igement. mematologic	I UNICILIES ANU INCIA	ieu Complications

Event	CTCAE Grade	Management/Action
		 If grade 4 thrombocytopenia recurs after restarting drug, pacritinib must be discontinued.
Hemorrhage	 Treatment-emergent grade 2 hemorrhage 	 Hold pacritinib for up to 7 days until hemorrhage resolves. Restart pacritinib at the same dose.
		• If event recurs, hold until resolution then restart at the next lower dose. If at 100 mg QD dose level, discontinue.
	■ grade 3	 Hold pacritinib for up to 7 days and start at the next lowest dose level once resolved. If at 100 mg QD dose level, discontinue.
	■ grade 4	Discontinue pacritinib
Febrile neutropenia	■ grade 4	 Hold pacritinib for up to 7 days and start at the next lowest dose level once resolved. If at 100 mg QD dose level, discontinue.
Neutropenic infections, including neutropenic sepsis	■ grade 4	 Hold pacritinib for up to 7 days and start at the next lowest dose level once resolved. If at 100 mg QD dose level, discontinue.

Table 3.	Treatment 7	Foxicity and	I Dosage	Management:	Hematologic	Toxicities and Related	Complications
----------	-------------	---------------------	----------	-------------	-------------	-------------------------------	---------------

Coagulation Testing

Coagulation testing will include PT, INR, PTT, and TT at screening, baseline, the end of Week 4, the end of Week 12, the end of Week 24, or the end of treatment visit, and 30 days after the last dose of study treatment. Additional coagulation testing should be done as clinically indicated.

These results will be taken into account, together with baseline platelet counts and prior medical history of bleeding, to help guide ongoing hematologic monitoring of platelet counts and clinical monitoring for bleeding. Pacritinib dosage modifications will be implemented for clinically significant AEs identified with this testing per the guidelines in Table 7.

6.5.3 Pacritinib Dosage Management Guidelines for QTc Interval Prolongation, Reduction in Ejection Fraction, and Other Cardiac Toxicities

A 12-lead ECG (collected in triplicate) will be checked at screening, baseline, the end of Week 4, the end of Week 12, the end of Week 24 or the end of treatment visit, including QTc calculation, and 30 days after the last dose of study treatment.

Ejection fraction will be checked (echocardiogram or MUGA scan) at screening, the end of Week 4, the end of Week 12, the end of Week 24, or the end of treatment visit, every 6 months during the follow up period, and 30 days after the last dose of study treatment. These assessments will be performed until approval of Amendment 6, at which point assessment ceases following the patient's End-of-Treatment, or 30-day post (EOT) visit as applicable. Pacritinib dosage modifications will be implemented for clinically significant ejection fraction changes as per Table 4 and Table 5. For patients with a grade 2 decreased

cardiac ejection fraction at baseline (LVEF 45%-50%), Table 5 should be used for any further decreases in LVEF. If pacritinib treatment is resumed after holding for ejection fraction abnormality, ejection fraction should be reassessed approximately 14 days later, then at least every 3 months as per the above schedule. Additional ejection fraction testing shall be done as clinically indicated.

Treatment should be modified as shown in the following table (Table 4), as recommended by FDA in case of QTc interval prolongation.

Table 4.	Pacritinib-Related QTc Prolongation, Decreased Cardiac Ejection Fraction and Other Cardiac
	Toxicities

CTCAE v4 Toxicity Grade	Management/Action		
1	No change.		
2 (First occurrence) For patients with grade 2 LVEF decreased at baseline (LVEF 45%-50%) and further decreases in LVEF on study, see Table 5)	 Hold pacritinib. If the toxicity resolves to grade ≤1 within 7 days, treatment may be resumed at the next lower dosage level (or discontinued, if toxicity occurred while taking 100 mg QD). Toxicity that does not resolve to grade ≤1 within 7 days requires treatment discontinuation. 		
2 (second occurrence)	Discontinue treatment.		
3	Discontinue treatment.		
4	Discontinue treatment.		

Abbreviations: CTCAE = Common Terminology Criteria for Adverse Events; LVEF = left ventricular ejection fraction; QD = once daily; QTc = corrected QT interval.

Table 5. Pacritinib-Related Decreased Cardiac Ejection Fraction for Patients with Grade 2 Ejection Fraction (LVEF 45%-50%) at Baseline

CTCAE v4.0 Toxicity Grade	Management/Action
3	Hold pacritinib for 1 week and reassess LVEF. If LVEF returns to baseline, patient may resume treatment at the next lower dose level; if grade 3 does not resolve, pacritinib should be discontinued.
4	Discontinue treatment.

Abbreviations: CTCAE = Common Terminology Criteria for Adverse Events; LVEF = left ventricular ejection fraction

In patients who resume pacritinib treatment after holding treatment for grade 2 QTc interval prolongation, follow-up ECGs (in triplicate) are recommended on Days 1, 7, 14, 28, and 56 after pacritinib restart. After restart of pacritinib, QTc monitoring should follow this schedule with ECGs obtained in triplicate:

- Restart Day 1 at 4 hours (± 1 hour) after ingestion of the first reduced dosage
- Restart Day 7 (\pm 2 days) 4 hours after dosing (\pm 1 hour)
- Restart Day 14 (± 2 days) 4 hours after dosing (± 1 hour)
- Restart Day 28 (± 2 days) at any time relative to dosing
- Restart Day 56 (± 7 days) at any time relative to dosing

If grade 2 toxicity does not resolve to grade ≤ 1 within 7 days, discontinue all treatment with pacritinib. If grade 2 toxicity recurs despite dosage reduction discontinue all treatment with pacritinib. For grade 3 and 4 QTc prolongation, discontinue all treatment with pacritinib.

Other Cardiac Toxicities

Discontinue treatment with pacritinib for all other grade 3 and 4 cardiac toxicities.

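### For a first fall from grade 3 to grade 4 platelets with a simultaneous grade 2 or 3 bleed, Section 6.5.2 read literally makes the hemorrhage row's required action optional

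*Protocol*

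**What the plan says.** Protocol Section 6.5.2 sets the status of the table: "Table 3 indicates required dose interruptions and modifications for hematologic toxicities and complications such as hemorrhage and febrile neutropenia". It then says how to handle overlap: "if more than one toxicity is experienced simultaneously, the higher-grade toxicity should determine the dose interruption/modification".

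Table 3 has two thrombocytopenia rows. The first needs a fall of at least two grades. The second is written "For patients starting treatment with grade 3 thrombocytopenia who progress to grade 4 thrombocytopenia" where that state either lasts at least 14 days or "is complicated by hemorrhage or a new platelet transfusion requirement". It gives no grade for the bleed. Its actions are:

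- Hold: "Pacritinib may be held for up to 7 days", at the physician's discretion and "until recovery of platelets to baseline".
- Restart: "Restart either at the same dose or at the next lower dose level".
- Recurrence: "If grade 4 thrombocytopenia recurs after restarting drug, pacritinib must be discontinued".

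The hemorrhage rows of the same table are firmer. A first grade 2 bleed requires a hold until it resolves, then restart at the same dose. A recurrent grade 2 bleed or a grade 3 bleed requires a hold until it resolves and then one dose level down, with discontinuation if the patient is already at 100 mg QD. A grade 4 bleed requires discontinuation.

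**The concern.** Followed as written, the rule weakens as toxicity worsens. If a patient who starts at grade 3 platelets stays there and has a grade 3 bleed, no thrombocytopenia row is triggered and the dose must come down. If the platelets also drop to grade 4, the second thrombocytopenia row takes over and the reduction is no longer required. That row itself names hemorrhage as a trigger, so the overlap is built into the table.

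The subject matters in this trial. Grade 3 or higher hemorrhage is a component of the primary safety measure (Protocol 11.1). Fatal intracranial hemorrhage was among the concerns behind the earlier Full Clinical Hold, and hemorrhage was more frequent at 200 mg BID, the top dose here, than at 400 mg QD (Protocol 1.3.4). The same section reports that bleeding risk did not appear to follow the degree of thrombocytopenia, which argues against letting a platelet rule displace the bleed's own rule. Section 6.5.2 also notes that patients with severe cytopenias may enroll, so the situation can arise.

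**Working it through.** The plan has no figure to reproduce. The check is a trace of Table 3 with the overlap sentence, for a first grade 4 platelet episode in a patient who started at grade 3.

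**Step 1: which thrombocytopenia row applies.** The fall is 4 − 3 = 1 grade, so the first row (at least 2 grades) does not apply. The second row does, because the episode is complicated by a bleed.

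**Step 2: which event governs.** Against a grade 2 bleed, 4 > 2; against a grade 3 bleed, 4 > 3. The thrombocytopenia row governs in both. Against a grade 4 bleed, 4 = 4, and the sentence gives no answer.

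**Step 3: what stops being required.** The dose ladder is taken as 200 mg BID, 100 mg BID, 100 mg QD (Protocol Table 2).

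| Bleed | Hemorrhage row requires | Governing row | No longer required | Cells |
|---|---|---|---|---|
| First grade 2 | Hold, same dose | Thrombocytopenia | Hold | 3 |
| Recurrent grade 2 | Hold, one level down; stop at 100 mg QD | Thrombocytopenia | Hold and reduction, or stop | 3 |
| Grade 3 | Hold, one level down; stop at 100 mg QD | Thrombocytopenia | Hold and reduction, or stop | 3 |
| Grade 4 | Stop | Tie | Not settled | 3 |

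- Reduction lost: 2 bleed types × 2 BID doses = 4 cells.
- Stop at 100 mg QD lost: 2 bleed types × 1 dose = 2 cells.
- Hold, with reduction or stop, lost: 4 + 2 = 6 cells.
- Hold only lost: 1 bleed type × 3 doses = 3 cells.
- Any required action made optional: 6 + 3 = 9 cells.
- Tie: 1 bleed type × 3 doses = 3 cells. Total: 9 + 3 = 12.
- Cells in which the stricter action is forbidden: 0.

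The cells are unweighted. They describe the rule, not how often each case occurs.

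**Step 4: dose in the 6 cells that lose a reduction or stop.** Daily doses come from SAP Section 9.

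| Current dose | Highest daily dose the thrombocytopenia row permits | Highest daily dose the hemorrhage row permits |
|---|---|---|
| 200 mg BID | 400 mg | 200 mg |
| 100 mg BID | 200 mg | 100 mg |
| 100 mg QD | 100 mg | 0 mg |

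**Step 5: does other text restore the requirement.**

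- Section 6.5.1 allows restart after two bleed-free days, but in the paragraph on invasive procedures. Even read broadly, it sets a waiting time, not a dose.
- The thrombocytopenia row's stop on recurrence depends on platelets, not on the bleed. It is stricter than the grade 3 hemorrhage row, which is why the trace covers a first episode only.
- The adjudication committee reviews bleeds from grade 4 upward (Section 2.2), and suspension of enrollment needs two hemorrhages of grade 4 or higher in one arm (Section 11.9). Neither reaches the bleeds in the 9 cells.

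**The case against.** The strongest reply is that the rows do not conflict. Table 3 is described as required and lists hemorrhage as its own event; the overlap sentence is introduced as a note and says only what should happen. The thrombocytopenia row allows the next lower dose, so at either BID dose a hold followed by a reduction satisfies both rows, and stopping at 100 mg QD is open to the investigator. The row may also be a deliberate allowance for patients who enter with severe thrombocytopenia and are described as having no alternative therapy. On that view the discretion comes from the row, not from the sentence.

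The window is also narrow. The toxicities must be simultaneous, and the platelets outrank the bleed only while they are at grade 4. Oversight is wider than the two grade 4 safeguards: the IDMC reviews bleeding about quarterly with no grade floor (Section 2.2), pharmacovigilance review is monthly (9.4.1), and the investigator (9.2) and medical monitor (4.2.1) can act at any time. Eligibility and concomitant-drug rules lower bleeding risk at entry and during treatment.

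Much of this stands. Compliance with the stricter row is always possible, and flexibility for low platelets alone is reasonable. Because the row itself names hemorrhage, changing the sentence alone would leave some ambiguity. But none of these provisions requires the reduction or the stop, and nothing says that the flexibility was meant to waive the bleed rule. A text open to both readings invites different handling across about 60 centers.

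**Conclusion.** The concern holds in this limited form: first fall from grade 3 to grade 4 platelets, simultaneous grade 2 or 3 bleed, literal reading of the overlap sentence. A required action becomes optional in 9 of 12 cells, with the reduction or stop lost in 6 of them. Severity is low to moderate. The number of patients affected cannot be derived from the documents.

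A reader might infer more than the documents support:

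- That the protocol directs same-dose restart after a serious bleed. It permits it; Section 6.5.1 makes resumption itself optional.
- That a patient with a grade 4 bleed may restart. The sentence is silent on the tie, and the discontinuation is best read as still binding because the table's actions are required.
- That earlier bleeding deaths arose from same-dose restarts. Nothing in the documents links them.
- That the primary safety measure is distorted. The dose chosen after the event does not change whether that event counts.

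Amendment 6 ends study treatment at Week 24, so the remaining benefit is for patients not yet at that point and for later protocols that reuse Table 3.

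**What to change.** Replace the overlap sentence in Section 6.5.2 with: *If more than one toxicity occurs simultaneously, the most restrictive applicable action governs.* This restores the hemorrhage action and settles the grade 4 tie.

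Add to the second thrombocytopenia row of Table 3: *Any grade 2 or higher hemorrhage is also managed by the hemorrhage rows; the stop for recurrent grade 4 thrombocytopenia still applies.*

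The cost is one sentence and one table line, with ethics approval at each site (Section 17) and regulatory approval if the change is classed as substantial. It is best bundled with another amendment. It needs no new data or patients. The clinical downside is a few more holds, reductions or discontinuations among bleeding patients with severe thrombocytopenia.
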